### **3.5.2 Deaths**

Death information for subjects in the Safety Analysis Set will be summarized by frequency (number and percentage) for the following:

- All deaths
- Deaths with a date of occurrence on or after the date of the first dose of study drug to on or before the date of the last dose of study drug plus 30 days
- Reason for Death

A subject-level listing will also be provided that includes the following information:

- Treatment group/cohort
- Last dose of study treatment (drug name and dose)
- Date of first dose of study treatment
- Date of last dose of study treatment
- Date of death
- Primary cause of death
- Preferred terms (PT) of any AEs with Fatal outcome
- PT of any Grade 5 AEs
- Whether or not the death occurred within 30 days after last dose of study treatment

- Flag for death due to COVID-19

### **3.5.3 Laboratory Data**

Laboratory data will be converted as needed to a standard set of units. Only lab values considered abnormal relative to baseline will be considered for the following.

Quantitative laboratory results reported as "< X", "<= X", "> X", or ">= X", will be converted to X for the purpose of severity grading, but will be presented as recorded in data listings.

Severity grades will be programmatically calculated using Journal of the American Medical Association (JAMA) ranges (Iverson 2007) and Common Terminology Criteria for Adverse Events (CTCAE) criteria (National Cancer Institute 2010) when available. Laboratory values considered to be normal by CTCAE criteria will be assigned a severity grade of 0. Laboratory values obtained more than 30 days after the last study drug administration will be included in listings but not in summary tables.

CTCAE severity grades will be summarized by shift tables for each hematology and chemistry parameter. The shift tables will display the number and percent of subjects by baseline severity grade and maximum post-baseline severity grade.

JAMA normal range categories (low, normal, or high) will be summarized by shift tables for each hematology and chemistry parameter. The shift tables will display the number and percent of subjects by baseline and post-baseline categories. Subjects will be counted in the post-baseline category of normal only if all post-baseline values are within the JAMA normal range. Subjects will be counted in the post-baseline category of high if at least one post-baseline value is above the JAMA normal range, and will be counted in the post-baseline category of low if at least one post-baseline value is below the JAMA normal range. Subjects having both low and high post-baseline values will be counted twice in the shift table.

All laboratory data will be displayed in listings. Values meeting CTCAE severity criteria, outside of JAMA normal ranges, or assessed as abnormal will be flagged in the listings.

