Hematology and serum chemistries will be summarized in a descriptive manner by calculating the mean, standard deviation, median, and range for baseline, minimum postbaseline value, maximum postbaseline value, average postbaseline value, and last postbaseline value. Laboratory values will be assigned toxicity grades when available using the NCI CTCAE scale and will be included as AEs if applicable. Directional shifts in laboratory toxicity grades (comparing baseline grade with worst postbaseline grade) will be analyzed using standard shift tables, presenting number and proportion of subjects and their maximum grade shift. Laboratory values taken during the PK sampling may be presented separately if appropriate; the final decision will be recorded in the SAP.

Vital signs will be summarized in a descriptive manner by calculating the mean, standard deviation, median, and range in the same manner described for laboratory

values. The results of the 12-lead ECG assessments will be summarized in the same manner as described for laboratories and vital signs.

The incidence, onset time, and titer of ADA will be summarized by descriptive statistics. The possible effects of ADA on PK (such as TTI-621 exposure as measured by  $C_{max}$  and AUC after seroconversion), efficacy, and safety of TTI-621 will be explored. Details will be provided in the SAP.

Prior and concomitant medications will be coded to the generic term using the current version of the World Health Organization Drug Dictionary and will be tabulated by cohort and listed by subject.

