### Safety Analysis Set

The Safety Analysis Set is the primary population for analyses of safety data and consists of all subjects who receive at least 1 dose of study treatment.

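### SAP 3.5.3 restricts laboratory data by an undefined criterion that contradicts the shift-table rules in the same section and in Protocol 8.4.4

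*SAP*

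**What the plan says.** After a line on unit conversion, SAP 3.5.3 (Laboratory Data) states: "Only lab values considered abnormal relative to baseline will be considered for the following". It does not say what makes a value abnormal relative to baseline, or which outputs the restriction covers.

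The same section then sets these rules:

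- Grading: "Laboratory values considered to be normal by CTCAE criteria will be assigned a severity grade of 0".
- CTCAE tables: "The shift tables will display the number and percent of subjects by baseline severity grade and maximum post-baseline severity grade".
- JAMA range tables: "Subjects will be counted in the post-baseline category of normal only if all post-baseline values are within the JAMA normal range". A subject is low or high if any post-baseline value lies outside the range on that side, and is counted twice if both occur.
- Timing: values taken more than 30 days after the last dose are listed but not summarized.
- Listings: "All laboratory data will be displayed in listings".

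Protocol 8.4.4 (Safety Analyses) says: "Directional shifts in laboratory toxicity grades (comparing baseline grade with worst postbaseline grade) will be analyzed using standard shift tables". It carries no abnormal-only restriction. On the population, SAP section 2 says: "The Safety Analysis Set is the primary population for analyses of safety data and consists of all subjects who receive at least 1 dose", and SAP 3.5 names that set for the safety analyses.

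**The concern.** A shift table works by showing every subject's starting category against the worst category reached, including those who stayed normal and those who did not change. The restriction is placed ahead of the grading and both kinds of shift table, and nothing limits its reach. A programmer who applies it loses data that the tables need. One who builds the tables as described has to ignore it.

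What is at stake is whether the tables are complete. Cytopenia is the toxicity of interest, and many of these subjects have diseases that lower blood counts. The Synopsis and Protocol 1.8.4 both say that the Grade 4 platelet decreases include events due to the underlying malignancy. The no-change cells show how much of the abnormality was there before treatment. The shift tables are also the only laboratory summaries in SAP 3.5.3; the rest is listings.

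**Working it through.** **Step 1. The plan's own figures.** The Synopsis and Protocol 1.8.4 report a safety analysis of 179 subjects at the 01 October 2018 data cut: 143 with an abnormal post-dose platelet count and 49 with a Grade 4 decrease.

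- 143/179 = 79.9%, given as 80%.
- 49/179 = 27.4%, given as 27%.

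Both reproduce.

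**Step 2. The restriction against each table rule.** The phrase has two plausible meanings. Reading A keeps post-baseline values that are abnormal. Reading B keeps post-baseline values that are worse than that subject's baseline, by grade or range category.

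- *Grade 0 for normal values.* Under A or B no normal value is left to grade, so the post-baseline Grade 0 column is empty.
- *Baseline grade by maximum post-baseline grade.* Under A, cells with a post-baseline grade of 1 or more survive. Under B only the worsening cells survive; the no-change diagonal and the improvement cells are empty.
- *JAMA normal category.* The rule needs all of a subject's post-baseline values. A subject whose values are all in range has none left, so the category is empty under A or B.
- *JAMA low and high.* These are judged against a fixed range, not against baseline. Under B, a subject who is low at baseline and stays low is counted by the table rule and removed by the restriction.
- *Baseline axis.* SAP section 3 defines baseline as the last value before first dose. That value cannot be abnormal relative to itself, so the axis has no data unless baseline is exempt, and no exemption is written.
- *Listings.* These take all laboratory data, so the restriction cannot apply to everything that follows it.

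**Step 3. What does not change.** If a subject's worst post-baseline grade is above baseline, that value is kept under either reading, and the maximum of the kept values is the same maximum. Subjects who worsened stay in the same cell.

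**Step 4. The percentages.** Take the 143 subjects with an abnormal post-dose count as a stand-in for those retained under Reading A.

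- Subjects with no retained value: 179 − 143 = 36, and 36/179 = 20.1%.
- Grade 4, denominator all treated subjects: 49/179 = 27.4%.
- Grade 4, denominator the subjects who remain: 49/143 = 34.3%.

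Under Reading B, subjects with an unchanged abnormal grade also lose their values. The documents give no count of them, so assume u such subjects, and assume all 49 Grade 4 subjects were worse than their own baseline. With the reduced denominator the result is 49/(143 − u):

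- u = 10: 49/133 = 36.8%
- u = 20: 49/123 = 39.8%
- u = 30: 49/113 = 43.4%

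With the full set as denominator the figure is 27.4% for each u.

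**The case against.** The strongest reply is that the sentence restricts values, not subjects. The population is fixed elsewhere as everyone who received a dose, and the section 3 conventions have categorical tables report the number in the denominator. Nothing in 3.5.3 says that percentages are taken among subjects with a retained value. This stands: a reader might infer that the plan inflates its laboratory percentages, but that needs a second step that the documents do not contain.

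The reply continues that the intended tables can be recovered. Grade 0, the normal category and the unrestricted listings all suggest that the authors did not mean to discard normal results. This also largely stands. It would be too strong to say that normal and unchanged subjects will be dropped. The programming specifications (SAP section 3) and the separate document on tables, figures and listings (SAP section 5) may settle the matter, but they are not available here. Even so, evident intent does not remove a written instruction that conflicts with it.

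Third, the effect on the safety assessment is limited. The primary endpoints are the incidence and severity of adverse events, with DLTs added for Parts 1 and 4 in the SAP. Thrombocytopenia, other cytopenias and anemia are summarized as adverse events of special interest. None of these outputs depends on the sentence, and no decision rule uses a shift table. This stands.

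**Conclusion.** The point holds as an undefined restriction that contradicts the table rules of its own section and departs from Protocol 8.4.4. Followed literally, it leaves the Grade 0 and normal post-baseline cells empty. If it means worse than baseline, the no-change and improvement cells are empty as well. A subject with a stable pre-existing cytopenia and one who stayed normal throughout would then be equally absent, and these tables could not separate pre-existing from new cytopenia.

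The effect on percentages is conditional. In the platelet illustration, Grade 4 moves from 27% to 34% if the denominator shrinks to the remaining subjects, and does not move if it is the full Safety Analysis Set. That illustration treats an abnormal post-dose count as equivalent to a criterion that the SAP leaves undefined.

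A reader might also infer that the worst grades shown would change. They would not for subjects who worsened (Step 3).

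**What to change.** Delete the sentence from SAP 3.5.3. In its place, state that both the CTCAE and the JAMA shift tables include all Safety Analysis Set subjects and use all post-baseline values up to 30 days after the last dose, which keeps the section's existing cut-off. Add a missing category on each axis for subjects without a baseline or without a post-baseline value, so that each table accounts for the whole set and the denominator is explicit.

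Moving the sentence to the listing flags would not help. The section already sets those flags by CTCAE criteria, the JAMA range or an assessment of abnormality, and none of these is relative to baseline.

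The cost is one deleted sentence and one or two added to the SAP. No further data collection is needed.

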## STATISTICAL METHODS:

### *Safety Analyses*

Safety analyses will be conducted using all dosed subjects. The results of the safety analyses will be presented by study phase. For the escalation phase, tabulations will be provided by dose cohort and overall. For the expansion phase, tabulations will be provided by disease cohort and overall. Some safety analyses may be performed based on all treated subjects combined.

TEAEs reported during the study will be tabulated and listed by MedDRA System Organ Class and preferred term. Tables will display number and percentage of subjects with the event for the following categories: all AEs, events considered related to study drug, events by severity, DLT, events occasioning treatment modification, and serious adverse events (SAEs). For the escalation phase, the observed DLT rate in each dose cohort will be calculated by the crude proportion of subjects who experienced DLT, accompanied with a 95% exact binomial CI.

Hematology and serum chemistries will be summarized using conventional summary statistics (mean, standard deviation, median, and range) for the following: baseline value, minimum and maximum post baseline values, average post baseline value, and last post baseline value. Standard shift tables will also be prepared presenting worst post baseline toxicity grade vs baseline. Incidence of subjects with ADA will be summarized descriptively. Laboratory values acquired during the immediate post-infusion period will be presented separately.

Vital signs and ECG results will be summarized in a descriptive manner by calculating the mean, standard deviation, median, and range by time point in the same manner described for laboratory values.

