### **3 Analyses and Summaries**

The statistical analyses performed for this study will be summarized by the following unless indicated otherwise:

- Initial assigned dose levels or initial assigned dosing schedules (in the case of Part 4 biweekly) for Part 1 and Part 4 (Dose Escalation cohorts)
- Monotherapy or combination therapy for Part 2 and Part 3
- Indication within monotherapy and by combination therapy for Part 2 and Part 3

The statistical analyses will be performed using SAS® version 9.2 or later (SAS Institute Inc., Cary NC). Programming specifications will be prepared which describe the datasets and variables created for this study. The datasets will be prepared using the most recent version of the Clinical Data Interchange Standards Consortium (CDISC) Study Data Tabulation Model (SDTM) and Analysis Dataset Model (ADaM). The source SDTM and ADaM datasets from which a statistical analysis is performed (including interim safety reviews) will be archived with the Sponsor.

The following data conventions will be employed in the study.

- Summary tables for continuous variables will contain the following statistics: N (number in population); n (number with data); mean; standard deviation; median; minimum; and maximum. Selected tables also may include 2-sided 95% confidence intervals (CIs) on the mean, calculated using a t-distribution approximation.
- Summary tables for categorical variables will include: N (number in denominator); n (number in numerator); and percent. Selected tables also may include 2-sided 95% CIs for the percent, calculated using the Clopper-Pearson method.
- Data from all study centers will be pooled for all analyses.
- The baseline value for a given parameter is the last value prior to the time of the first dose. A value is considered to be post-baseline if it is obtained after the time of the first dose.
- Study Day is defined as Calendar Date – Date of First Treatment + 1 if the calendar date is on or after the date of the first treatment, and Calendar Date – Date of First Treatment if the calendar date is before the date of the first treatment.
- Partial dates will be displayed as partial dates in listings and missing dates will be displayed as missing. The corresponding Study Day for partial or missing dates will be displayed as missing in listings.
- Unless specifically noted later in this SAP, missing data will not be imputed.

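### SAP 3.5.3 does not record whether post-infusion laboratory values are shown separately, and its shift tables cannot separate a transient platelet fall from one that persists to the next dose

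*SAP*

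**What the plan says.** The Protocol speaks twice on this point, with different force. The synopsis, under Safety Analyses, is unconditional: "Laboratory values acquired during the immediate post-infusion period will be presented separately". Protocol 8.4.4 is permissive and delegates: "Laboratory values taken during the PK sampling may be presented separately if appropriate; the final decision will be recorded in the SAP".

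SAP 3.5.3 plans two shift tables for each hematology and chemistry parameter. For CTCAE grade, "The shift tables will display the number and percent of subjects by baseline severity grade and maximum post-baseline severity grade". For the JAMA range, a subject counts as low if any single post-baseline value is below the range. SAP section 3 defines the term: "A value is considered to be post-baseline if it is obtained after the time of the first dose". The only exclusion by timing in SAP 3.5.3 is at the far end: "Laboratory values obtained more than 30 days after the last study drug administration will be included in listings but not in summary tables". A further sentence limits attention to values abnormal relative to baseline, but says nothing about time since infusion. The section also states: "All laboratory data will be displayed in listings".

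Protocol 8.4.4 further describes numerical summaries, namely mean, standard deviation, "median, and range for baseline, minimum postbaseline value, maximum postbaseline value, average postbaseline value, and last postbaseline value", and the synopsis says the same. SAP 3.5.3 contains none of them.

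**The concern.** Timing relative to the infusion is the main feature of the platelet signal in this trial. Protocol 1.8.4 describes counts that drop on the dosing day and have generally recovered by the following dose, with stable pre-infusion counts. It gives median pre-dose and post-dose platelet values of 257 and 123 at 0.2 mg/kg, and 234 and 188 at 0.5 mg/kg. The revised Part 4 DLT rule rests on that pattern: Grade 4 thrombocytopenia now counts only if it lasts more than 72 hours, or if the count reaches 10 × 10⁹/L or lower.

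A worst-grade table that mixes draws made hours after infusion with draws made a week later will largely reflect the nadir. It can show how deep the falls were. It cannot show whether they had resolved by the next dose. The final report would then have no laboratory summary table that bears on the trial's central safety argument, although the synopsis promised one.

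**Working it through.** No sample size, power or error rate is involved, so the check compares the texts and then tests the stated consequence.

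**Step 1: was the decision made?** The synopsis says the separate display will be produced. Protocol 8.4.4 says it may be, and that "the final decision will be recorded in the SAP". SAP 3.5.3 neither plans the display nor says it was considered unnecessary. On either Protocol reading, something that should be in the SAP is absent.

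**Step 2: does the SAP pool the values?** It does not say so in words, but the rules lead there. Post-baseline means any time after the first dose. The only timing exclusion is more than 30 days after the last dose. The CTCAE table takes the maximum grade, and the JAMA table takes any value out of range. So a 4-hour count and a pre-dose count a week later compete for the same cell.

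**Step 3: what does pooling hide?** Assumed platelet counts (× 10⁹/L), for illustration only. Grade 4 is below 25, as in the Protocol; 200 is taken as Grade 0 and within the normal range.

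| Profile | Baseline | 4 h | 24 h | Next pre-dose | Following pre-dose |
|---|---|---|---|---|---|
| Transient | 200 | 20 | 60 | 200 | 200 |
| Sustained | 200 | 20 | 20 | 22 | 24 |

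- SAP CTCAE table: both are Grade 0 to Grade 4.
- SAP JAMA table: both are normal to low.
- Pre-dose values only: transient is Grade 0 to 0; sustained is Grade 0 to 4.

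**Step 4: would the omitted summaries help?** On the same profiles:
- Minimum: 20 and 20, no separation.
- Average: (20 + 60 + 200 + 200)/4 = 120 against (20 + 20 + 22 + 24)/4 = 21.5.
- Last: 200 against 24.

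The average and last values would partly show recovery, so leaving them out widens the gap.

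**Step 5: do AE records cover it?** Protocol 1.8.4 reports abnormal post-dose platelet counts in 143/179 = 79.9% and Grade 4 decreases in 49/179 = 27.4%. Protocol 9.5 reports thrombocytopenia or decreased-platelet AEs in 47/179 = 26.3%. Even if all 47 are among the 143, at least 143 − 47 = 96 subjects had an abnormal count with no such AE, and so no AE dates from which to read duration. These percentages show how common abnormal counts are. They do not measure the effect of pooling, because they are not split by draw time and the Grade 4 figure includes falls due to the underlying malignancy.

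**The case against.** The strongest reply is that Protocol 8.4.4 allows the SAP not to separate these values, that worst-grade shift tables are conventional, and that other outputs address persistence. All laboratory values are listed and abnormal ones flagged (SAP 3.5.3). AE start and end dates are collected (SAP 3.5.1). DLTs are summarized and listed, with a duration element in Part 4. Dose interruptions are tabulated by reason (SAP 3.4), and redosing has a platelet threshold (Protocol 6.5.2), so a sustained fall can surface there. Platelet transfusions are summarized (SAP 3.5.5). SAP section 5 also keeps the list of tables in a separate document, which is not available here. Finally, the DLT revision was argued from 2018 data already examined before and after dosing.

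Much of this stands, and it rules out three stronger readings.

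- A reader might infer that the SAP breaches the Protocol. It conflicts with the synopsis, but under 8.4.4 its fault is only that it leaves the decision unrecorded.
- A reader might infer that transient and sustained falls cannot be told apart anywhere in the report. That is true only of the laboratory summary tables.
- A reader might infer that heavier sampling makes Part 4 look worse than Part 3. The documents do not support this. Part 4 schedules 5 + 1 + 1 = 7 post-infusion hematology draws. A Part 3 subject who completes the ramp from 0.2 to 0.5 mg/kg has 3 in Week 1 plus one at each of 3 increases, so 6 (Protocol 7.3 and 7.6, Appendix D). Table 7-1 also leaves it unclear whether Part 3 has a 24-hour draw. SAP 1.2.6 produces separate output sets by part, and no cross-part laboratory comparison is planned.

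The reply does not close the gap. Listings do not summarize. DLT summaries cover only Part 1 and the weekly Part 4 cohorts, and the Part 1 Grade 4 platelet criterion has no duration element. At the October 2018 cutoff, 161 of 179 subjects were in the expansion phase.

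**Conclusion.** The point holds as a reporting gap that is cheap to close. The two Protocol statements differ, the SAP does not record the decision assigned to it, and its laboratory summary tables pool values in a way that hides recovery before the next dose. No design figure, decision rule or primary endpoint changes.

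The conclusion rests on two assumptions: that the SAP's definition of post-baseline applies to the shift tables as written, and that the separate table list adds no split by time from infusion. If that list already contains one, what remains is to reconcile the Protocol wording and record the decision.

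**What to change.** 1. Reconcile the synopsis sentence with Protocol 8.4.4, and state the decision in SAP 3.5.3.
2. Keep the overall worst-grade shift table.
3. Add two hematology shift tables: one for pre-dose samples, and one for immediate post-infusion samples (end of infusion to 4 hours). Show Day 2 and Day 4 values separately where collected, so that counts at about 24 and 72 hours are not merged with the early nadir. State how unscheduled repeat counts are classified.
4. Restore the minimum, maximum, average and last post-baseline summaries.
5. Do not let the pre-dose table replace the overall or post-infusion table when dose levels are compared. It would drop the acute nadirs, and a very low count at any time is itself a DLT criterion in Part 4.

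The cost is a short SAP paragraph, a wording alignment in the Protocol, and one extra set of tables from data already collected.
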